5.2.1.1.2 Calculation of Number of Years, Months, and Weeks

In this statistical analysis plan, the number of years, months, and weeks will be consistently calculated using the following formulas:

- Number of years = Number of days / 365.25
- Number of months = Number of days / 30.4375
- Number of weeks = Number of days / 7

The number of years, months, or weeks will not be rounded unless indicated.

5.2.1.1.3 Acceptable Time Window

For each evaluation time point, data obtained within the time window specified below will be used. If multiple observations or measurements are available within a time window, data outside the time window will be excluded, and then the data obtained on the day closest to the scheduled day will be used for each parameter of observation or measurement. If measurement days before and after the scheduled day are shifted by the same number of days, the data obtained after the scheduled day will be used.

[Imaging assessment (overall response)] The reference day is the randomization day.

Time point	Scheduled day	Time window
6 weeks after randomization	Day 43	Randomization day \leq measurement day \leq Day 50
$n \times 6$ weeks after randomization	Day ($n \times 42 + 1$)	Day ($n \times 42 - 6$) \leq measurement day \leq Day ($n \times 42 + 8$)

[Sum of diameters of target lesions/laboratory values/tumor markers/vital signs (including height/weight/BSA)]

Time point	Scheduled day	Time window
Baseline	Start date of study treatment	Measurement day \leq start date of study treatment

[Cycles used for the analyses]

Relationship between the start date of treatment in each cycle and the assessment day	Cycle used for the analysis
Start date of treatment in Cycle $x <$ assessment day $<$ start date of treatment in Cycle $x + 1$	Cycle x
Start date of treatment in Cycle $x =$ assessment day and assessed after treatment	Cycle x
Start date of treatment in Cycle $x =$ assessment day and examined before treatment	Cycle $x - 1$ If $x = 1$, then baseline is used.
Start date of treatment in Cycle $x <$ assessment day (with no next cycle) within the cycle decision period*	Cycle x
Start date of treatment in Cycle $x <$ assessment day (with no next cycle) outside the cycle decision period*	After safety follow-up

*Data obtained on the date of the last study treatment + 30 days or the start date of subsequent therapy, whichever comes first (including the day), will be included in the cycle decision period. Data obtained within this period after the date of the last study treatment will be included in the last cycle.

When data are collected in each cycle that is not specified in the list, all cycles except those after safety follow-up will be included in the analysis.

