6.1.1 Definition of Study Period

Study periods for each patient are defined below:

- Pretreatment Period: Commences on the day the ICF is signed and lasts until the day prior to initiation study treatment.
- Study Treatment Period: Commences on the day of initiation study treatment and lasts until the day the patient meets any of the study treatment discontinuation criteria (see. 13.1.1 Study Treatment Discontinuation Criteria).
- Safety Follow-up Period: Defined as the day after the end of study treatment (i.e. last dose of study drug) until 30 days or until the start of new anti-tumor therapy, whichever comes first. (see. 13.1.2 Safety Follow-up Discontinuation Criteria).
- Tumor Follow-up Period: Applicable only to patients who have had no progressive disease (PD) defined by RECIST version 1.1 until the end of study treatment and defined as the day after the end of study treatment until patients meet tumor follow-up discontinuation criteria (see. 13.1.3 Tumor Follow-up Discontinuation Criteria).
- Survival Follow-up Period: Defined as the day after the end of study treatment until patients meet survival follow-up discontinuation criteria (see. 13.1.4 Survival Follow-up Discontinuation Criteria). The patient will be followed for survival and the use of new anti-tumor therapy.
- Post-Treatment Follow-up Period: Defined as the day after the end of study treatment.

7. Study Drug

The sponsor will supply TAS-118 (30, 40, 50, 60 mg), S-1 (20, 25 mg), L-OHP (100 mg), CDDP (50 mg) during study period.

[figure not shown]
[figure not shown]
[figure not shown]
[figure not shown]
TAS-118 will be packed in sachet packages in a box. S-1 will be packed in a press through package (PTP) in a box.

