- Every 1 week starting on Day 1 of each treatment cycle if the next treatment cycle is delayed (the data may be collected within 7 days before the scheduled date). Examination is mandatory on Day 1 or the day before starting the study treatment specified in this protocol.
- End of treatment assessments must be completed within 14 days from the date of last dose of study drug.
- These data may be collected 30 days after last dose of study drug or until the start of new anti-tumor therapy, whichever comes first. In cases an AE/SAE related to study drug is not resolving, the safety follow-up period will be extended.
- Obtain survival status (alive/ dead) at scheduled 12-week time intervals from randomization until death, and at the cutoff date for second interim analysis and primary evaluation (the data may be collected within 2 weeks before or after the scheduled date).

Table 11.2-2 A Study Schedule Arm B (S-1/CDDP)

Procedure	Pretreatment Period				Study Treatment Period				Post-treatment Follow-up Period			
	within 28 days prior to randomization	within 21 days prior to randomization	within 14 days prior to randomization	within 7 days prior to Day 1 of the first treatment cycle ^c	Arm B				End of Treatment ^m (+14 days)	Safety Follow-up ⁿ 30 days after last dose of study treatment (+14 days)	Tumor Follow-up Every 6 weeks (+/- 1 week)	Survival Follow-up Every 12 weeks (+/- 2 weeks)
					Day 1	Day 8 ⁱ (Day 6 to 15) (Japan)	Day 15 ^j (Day 8 to 22)	Before Initiation of next treatment cycle ^{k,1} Day36 (Day 29 to 43)				
S-1 treatment					X ^f (Day 1 - 21)							
CDDP treatment (Korea)					X ^f							
CDDP treatment (Japan)						X ^g						
Signed ICF	X											
Patient Background	X											
Height			X									
Pregnancy Test ^a			X									
Weight			X	X				→ ^h	X	X		
ECOG PS			X	X				→ ^h	X	X		
Blood Pressure			X	X				→ ^h		→ ^h		
Body Temperature			X	X				→ ^h		→ ^h		
ECG			X					→ ^h		→ ^h		
Physical Examination			X	X		X ⁱ	X	X	X	X		
Hematology			X	X		X ⁱ	X	X	X	X		
Serum Chemistry ^b			X	X		X ⁱ	X	X	X	X		
Urinalysis ^b			X	X		X ⁱ	X	X	X	X		
Tumor Markers ^c			X	→	→	→	→	→	→	→	X	
Tumor Measurements ^c		X		→	→	→	→	→	→	→	X	
Concomitant Medications ^d		X		→	→	→	→	→	→	X		
AE/SAE Assessment ^d		X		→	→	→	→	→	→	X		
Post Treatment												X
Survival Status					→	→	→	→	→	→	→	X ^o

- a. If the patient is female and of childbearing potential, a pregnancy test (serum or urine) must be done and the results must be negative at baseline.

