11.6 Safety Follow-up

A Safety Follow-up visit will be conducted 30 days (+ 14 days) after the last dose of study drug. Moreover, if an adverse drug reaction due to the study drug occurs after the end of the safety follow-up period, this information should be reported. If the patient starts new anti-tumor therapy within 30 days of the last dose of study treatment, the Safety Follow-up Visit should be performed prior to the start of new anti-tumor therapy. If the patient is unable to return to the site prior to the initiation of new treatment, a follow-up phone call can be

conducted by the site to collect any new safety information that occurred between the “11.5 End of Treatment Visit” and the initiation of the new treatment.

Perform the following assessments:

- ECOG PS, weight, physical examination, hematology, serum chemistry, urinalysis, AE/SAE assessment, concomitant medications (including new anti-tumor therapy)

As needed (when abnormalities are indicated):

- Body temperature, blood pressure, electrocardiography

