- Measurement date of grade 2 or less reduction in laboratory values – date of the last study treatment ≥ 30 days

When the start date of subsequent therapy \leq date of the last study treatment + 30 days is met, the following criterion will be used:

Measurement date of grade 2 or less reduction in laboratory values \geq start date of subsequent therapy

- After “grade 3 or higher reduction” is replaced with “grade 2 or higher reduction” and “recovery to grade 2 or less” is replaced with “recovery to grade 1 or less,” the same analyses as specified above will be conducted.

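### SAP 5.2.1.1.3 and 7.9 contradict each other on the boundary day of the last cycle, and for laboratory data both stop short of the protocol's day 30 to 44 safety visit

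*SAP*

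**What the plan says.** **Protocol, visit.** Section 11.6 states: "A Safety Follow-up visit will be conducted 30 days (+ 14 days) after the last dose of study drug". The allowance is one-sided. Hematology, serum chemistry and urinalysis are among the required assessments. If new therapy begins within 30 days, "the Safety Follow-up Visit should be performed prior to the start of new anti-tumor therapy".

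**Protocol, period.** Section 6.1.1 gives the safety follow-up period a 30-day end, or the start of new therapy if sooner. Sections 13.1.2 and 15.1.1 use the same limit. A footnote to the schedule tables in 11.2 adds: "In cases an AE/SAE related to study drug is not resolving, the safety follow-up period will be extended".

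**SAP 5.2.1.1.3.** The cycle decision period is set by "Data obtained on the date of the last study treatment + 30 days or the start date of subsequent therapy, whichever comes first", and the text adds that the boundary day is included. Post-treatment data inside the period belong to the last cycle. Later data are labelled as falling after safety follow-up. By default, "all cycles except those after safety follow-up will be included in the analysis".

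**SAP 7.9.** For hemoglobin, white cells, neutrophils and platelets, the SAP summarizes time from the lowest value to grade 2 or less within the cycle of onset, in subjects with a grade 3 or higher reduction. A subject counts as not recovered if any listed criterion is met. One is that no grade 2 or lower value is measured in the same cycle. Another is "Measurement date of grade 2 or less reduction in laboratory values – date of the last study treatment ≥ 30 days". When subsequent therapy starts within 30 days of last treatment, that limit is replaced by a measurement date on or after the start of that therapy. The whole analysis is repeated for grade 2 or higher, with recovery to grade 1 or less.

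**The concern.** The two SAP sections share one boundary but treat it in opposite ways. Section 5.2.1.1.3 keeps the boundary day in the last cycle, and 7.9 rejects a recovery measured on it. The conflict falls on dates when a sample is likely to be taken: day 30 is the nominal safety visit, and a sample drawn before dosing on the day new therapy starts carries that day's date.

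The protocol also lets the safety visit take place up to day 44, while the SAP's laboratory window ends at day 30. A compliant visit on days 31 to 44 yields values that do not enter the last-cycle laboratory summaries, and a recovery first seen there cannot count.

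At stake is the description of recovery from cytopenia after the final cycle, which includes patients who stopped for toxicity. A documented recovery would be reported as a failure to recover.

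**Working it through.** The plan states no figure to reproduce here. The check applies each rule, as written, to each permitted visit day.

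**Inputs**
- d = measurement date minus date of last study treatment.
- s = start date of subsequent therapy minus date of last study treatment (no upper limit if none is given).
- b = min(30, s).
- Protocol 11.6: with no new therapy within 30 days, d runs from 30 to 30 + 14 = 44. That is 44 − 30 + 1 = 15 permitted days.
- SAP 5.2.1.1.3: in the last cycle if d ≤ b.
- SAP 7.9, time criterion: not recovered if d ≥ 30 when s > 30, and if d ≥ s when s ≤ 30. Both cases reduce to d ≥ b.

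**1. The two SAP rules against each other.** Both d ≤ b and d ≥ b hold only at d = b. So every treated patient has exactly one date on which the sections conflict: day 30, or the start of subsequent therapy if that comes first.

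The SAP's inclusive day count (5.2.1.1.1) does not remove the conflict, because 7.9 writes a plain date difference. Adding 1 would give d + 1 ≥ 30, that is d ≥ 29, and would widen the conflict to days 29 and 30.

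**2. The SAP rules against the visit window** (assuming no subsequent therapy by the visit date)

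| Visit day d | In last cycle (5.2.1.1.3) | Recovery first seen then (7.9) |
|---|---|---|
| 30 | yes | not recovered (time criterion) |
| 31 to 44 | no | not recovered (time and same-cycle criteria) |

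- Days outside the last cycle: 14 of 15, or 14/15 = 93%.
- Days on which a first-seen recovery fails: 15 of 15.
- Days on which the two sections contradict each other: 1 of 15 (day 30).

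**3. After each change**
- Strict inequalities in 7.9 (d > b): day 30 counts, so a recovery can count on 1 of 15 days and the contradiction is gone.
- Both laboratory cutoffs at min(44, s), with d > cutoff as not recovered: 15 of 15 days are kept and none is forced to not recovered.

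**4. What a 44-day cutoff does to the last cycle** (assuming full dosing, with last treatment on day 7 in Arm A and day 21 in Arm B)
- Arm A, 14-day cycle: 7 + 30 = day 37 (37/14 = 2.6 cycle lengths) becomes 7 + 44 = day 51 (51/14 = 3.6).
- Arm B, 35-day cycle: 21 + 30 = day 51 (51/35 = 1.5) becomes 21 + 44 = day 65 (65/35 = 1.9).

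**The case against.** The strongest defense is that 30 days is the protocol's own limit. The safety follow-up period and the adverse event window both end there, and the SAP's label for later data follows that definition. The looseness then lies between the protocol's period and its visit allowance, and ending the laboratory window at 44 days is only one way to resolve it. It would make the laboratory and adverse event windows differ. SAP 7.9 also measures recovery within a cycle, and step 4 shows that the last cycle already runs well past its nominal length, proportionally more in Arm A.

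This carries weight against treating the 44-day change as mandatory. It does not explain why 7.9 rejects day 30, which lies within both the protocol period and the SAP's last cycle.

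Some stronger readings are tempting but not supported:
- *The SAP discards on-time safety visits in general.* Day-30 visits, and visits brought forward before new therapy, stay in the last cycle.
- *Late toxicity disappears.* Adverse event tables use treatment-emergent events (SAP 5.1.2.1, 7.2.1), and clinically significant laboratory abnormalities must be reported as adverse events (Protocol 15.2.1). Clinical-findings recovery (SAP 7.10) states no 30-day limit. Weight and performance status are summarized at discontinuation (SAP 7.12).
- *The figure of 93% describes patients.* It is a share of calendar days. Recoveries seen at the end-of-treatment visit, or in any other last-cycle sample before the boundary, still count.
- *The comparison between arms is biased.* Retention does depend on when new therapy starts, but nothing in the documents shows that this differs by arm.
- *Recoveries found during extended follow-up should all count.* That extension has no fixed end and does not fit a within-cycle measure.

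**Conclusion.** The point holds in two parts of unequal strength.

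The first is a plain contradiction. SAP 5.2.1.1.3 includes the boundary day and 7.9 rejects a hematology recovery measured on it, although that day can be the protocol's nominal safety visit. This needs correcting whatever view is taken of the window's length.

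The second is a mismatch with the visit schedule: 14 of 15 permitted visit days lie outside the laboratory window. Aligning them is reasonable but open to debate, given the protocol's 30-day safety period.

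The consequence is small. It reaches descriptive last-cycle laboratory summaries and the recovery summaries for four hematology tests (grade 3 or higher, and the grade 2 or higher repeat). Overall survival, alpha, power, adverse event tables and clinical-findings recovery are untouched. The day counts assume no subsequent therapy before the visit. The number of patients affected cannot be computed from the documents.

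**What to change.** **Minimum.** In SAP 7.9, change ≥ 30 days to > 30 days, and change the measurement date being ≥ the start of subsequent therapy to > that start. Both then agree with 5.2.1.1.3. The cost is two inequality signs in the text and in the code.

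**Preferred addition.** End the laboratory cycle decision period in 5.2.1.1.3 and the 7.9 cutoff at last treatment + 44 days, or at the start of subsequent therapy if earlier. Move them together, because the same-cycle criterion in 7.9 would otherwise still reject days 31 to 44. The condition in 7.9 that switches to the subsequent-therapy rule must move from 30 to 44 days as well. Leave the 30-day adverse event window as it is.

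The cost is a longer last cycle for laboratory data, proportionally more in Arm A, and a laboratory window that differs from the adverse event window. If the sponsor keeps 30 days, the SAP should say that laboratory values from visits on days 31 to 44 are left out of these summaries, and why.

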5.2.1.2 Handling of Missing Data and Abnormal Values

No imputation of missing data will be performed. All data accepted at each time point will be used for the analysis. The proportion of subjects with adverse events and other proportions will be calculated using the analysis population as the denominator.

All data measured will be used for the analysis unless the cause of abnormalities is obvious, such as laboratory abnormalities caused by hemolysis during blood collection. If there are abnormalities to be

excluded from the analysis, these values will be identified, and the reason for exclusion will be justified.

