16.2.2 Criteria for Handling Patient Data

The criteria for handling patient data are described below.

The sponsor, in collaboration with the medical specialists, will determine the approach to handle data if there are problematic patients for handling except the criteria listed below:

(1) Handling of missing values and abnormal values

- No specific measures will be implemented. Analyses will be performed using all the data gathered for each time frame. For each analysis proportions will be estimated on the basis of the whole population analyzed.
- The analyses will include all data points unless the laboratory tests, such as the effect of hemolysis during blood collection, showed obvious abnormal values. In the presence of excluding abnormal laboratory results from analysis, these values will still be provided and the reasons for exclusion clearly stated.

(2) Patients with violations of study drug randomization

- For those analyses involving the AT population, the data of patients who have been administered study drug of different treatment arm from allocated treatment arm will be treated as that arms based on actual administered study drug.
- In the analyses for FAS or TR population, data will be treated as allocated treatment arm.

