5.2.2. Patient Baseline Characteristics

A list of patient baseline characteristics to be measured at entry is presented in Table 5-6.

For ECOG PS, both data obtained at randomization and data entered in “Vital Signs and ECOG (At the time of Randomization)” of the CRF will be used.

For the presence or absence of measurable lesions, both data obtained at randomization and data entered in “Tumor Imaging (Baseline)” of the CRF will be used. In the data from “Tumor Imaging (Baseline),” a measurable lesion is determined as being present when a target lesion is present, and a measurable lesion is determined as being absent when a target lesion is absent.

The number of metastatic organs is defined as the number of “sites of lesions” recorded in “Target Lesion” and “Non-target Lesion” at predose. However, “Stomach” will not be treated as a metastatic organ because all stomach lesions are primary lesions. The number of metastatic organs will be counted as one if multiple metastases are recorded in the same organ, and regional lymph nodes and distant lymph nodes are counted as the same organ. Metastatic organs recorded as “Other” will also be counted respectively in “Number of metastatic organs.”

If multiple measurements are available before treatment initiation, the most recent data before treatment initiation will be used.

Among the patient characteristic factors listed in Table 5-6, the factors used for efficacy analysis are presented in Table 5-7, and the details of categories of each factor are presented in Table 5-8.

If data are missing, the category will be indicated as “Missing.” Missing data will be excluded from the denominator used to calculate proportions and from statistical tests.

Table 5-6 Characteristic factors

Parameter	Factor
Patient baseline characteristics	Sex, age, race, country, height, weight, BSA, ECOG PS
Disease characteristics	Presence/absence of primary lesion, primary site, histological type, detail of diffuse type, detail of intestinal type, HER2, clinical stage, presence/absence of measurable lesion, sum of diameters of target lesions, category of the number of metastatic organs, metastatic organ category, presence/absence of liver metastasis, peritoneum metastasis, ascites, and lymph node metastasis, JCOG Index*

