5.2.3.2 Proportion

Proportions will be calculated using the following formula:

$$\text{Proportion (\%)} = \frac{\text{Number of relevant subjects}}{\text{Number of subjects in each arm in the analysis population}} \times 100$$

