7.6. Compliance Analyses

The following analyses will be conducted in the AT and FAS populations. These analyses except listings will also be conducted by country.

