7.6.2. Compliance

- The number and proportion of subjects with dose reduction, interruption, skip (only for L-OHP and CDDP), and prolongation of the recovery period (only for TAS-118 and S-1) will be calculated in each treatment arm. These analyses will be conducted for each cycle and for the overall cycles.

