7.6.6. Treatment Cycle

- The summary statistics of the number of subjects in each cycle and the last cycle number in each subject will be presented by treatment arm.

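### The by-cycle dose-modification proportions in SAP 7.6.2 use the whole arm as denominator, so subjects who never started a cycle count as event-free and later-cycle rates are understated

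*SAP*

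**What the plan says.** SAP 5.2.1.2 sets a general rule: "The proportion of subjects with adverse events and other proportions will be calculated using the analysis population as the denominator". The formula in SAP 5.2.3.2 has the same denominator, "Number of subjects in each arm in the analysis population". Protocol 16.2.2 points the same way, less exactly: "For each analysis proportions will be estimated on the basis of the whole population analyzed".

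SAP 7.6.2 asks for "The number and proportion of subjects with dose reduction, interruption, skip (only for L-OHP and CDDP), and prolongation of the recovery period" and adds: "These analyses will be conducted for each cycle and for the overall cycles". The lead-in to SAP 7.6 fixes the populations: "The following analyses will be conducted in the AT and FAS populations". Neither place gives a different denominator for the by-cycle figures.

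Two other places matter. For baseline characteristics, SAP 5.2.2 makes an explicit exception: "Missing data will be excluded from the denominator used to calculate proportions and from statistical tests". SAP 7.6.6 reports, by arm, "The summary statistics of the number of subjects in each cycle".

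**The concern.** A subject can have a dose reduction, interruption, skip or prolonged recovery in cycle k only after starting cycle k. Under protocol 13.1.1, treatment ends at progression, for an adverse event, at the patient's request and for other reasons, so the number starting each cycle falls steadily. With a fixed denominator, those who have left treatment are counted as having had no modification.

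A constant risk per treated cycle would then print as a falling rate, and the table would suggest that tolerability improves with time when the denominator has simply not followed the patients. Because the arms differ in cycle length and probably in time on treatment, the understatement at a given cycle number also differs between them.

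**Working it through.** The plan states no by-cycle rate and no time on treatment, so there is no figure of its own to reproduce.

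**Relation.** Let S(k) be the share of the arm that starts cycle k, and r(k) the rate among those who start it. The whole-arm proportion is S(k) × r(k), so the relative understatement is 1 − S(k), whatever r(k) is. Both populations require at least one dose, so S(1) = 1 and cycle 1 is correct. S(k) cannot rise with k, so the understatement never shrinks.

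**Inputs.**
- Cycle length: 14 days in Arm A (protocol 10.1.2.1) and 35 days in Arm B (10.1.2.2 and 10.1.2.3). Arm B recovery may be shortened from 14 to 7 days, giving 28-day cycles.
- Days per month: 30.4375 (SAP 5.2.1.1.2).
- Time on treatment (assumption): exponential, with the phase II PFS medians in protocol 2.4 as proxy: 8.3 months for S-1/LV/L-OHP (Arm A) and 5.6 months for S-1/CDDP (Arm B).
- Ranges of medians (assumption): 4 to 10 months in Arm A, 4 to 8.3 months in Arm B.

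**Formula.** S(k) = 2^(−t/median), with t = (k − 1) × cycle length / 30.4375.

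Example, Arm B cycle 6: t = 5 × 35 / 30.4375 = 5.75 months; S = 2^(−5.75/5.6) = 0.491; understatement 50.9%.

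| Arm, cycle | t (months) | S(k) | Understatement | Over the range of medians |
|---|---|---|---|---|
| A, 2 | 0.46 | 0.962 | 3.8% | 3.1% to 7.7% |
| A, 6 | 2.30 | 0.825 | 17.5% | 14.7% to 32.9% |
| A, 13 | 5.52 | 0.631 | 36.9% | 31.8% to 61.6% |
| B, 2 | 1.15 | 0.867 | 13.3% | 9.2% to 18.1% |
| B, 4 | 3.45 | 0.652 | 34.8% | 25.0% to 45.0% |
| B, 6 | 5.75 | 0.491 | 50.9% | 38.1% to 63.1% |

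If every Arm B cycle took 28 days, the ranges would be 7.4% to 14.7% at cycle 2 and 31.9% to 54.9% at cycle 6.

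**In counts.** Take the FAS target of 325 per arm and an assumed 20% rate among those treated. At Arm B cycle 6, 325 × 0.491 ≈ 160 subjects start the cycle and 0.20 × 160 = 32 have the event. The rule in the SAP prints 32/325 = 9.8%; the rate among those at risk is 32/160 = 20%.

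**The case against.** The strongest reply is that the information is not lost. SAP 7.6.2 reports counts as well as proportions, and 7.6.6 reports how many subjects are in each cycle, so a reader can divide one by the other. SAP section 9 also defers the full list of analyses to a separate output plan, which may specify table layouts. Protocol 16.2.2 can be read as the population of that particular analysis. And protocol 16.3.3.2 lists only discontinuation and dose intensity under treatment status, so the by-cycle table is an addition by the SAP with no test attached.

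This limits the importance of the point but does not remove it. The counts in 7.6.6 do not correct the percentages printed under 7.6.2. The output plan is not among the documents, and the SAP as written gives a rule that leads to the whole arm. SAP 5.2.2 shows that the authors wrote an exception where they wanted one.

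A reader might infer more than the documents support:
- *Every proportion in the report is affected.* It is not. Baseline proportions have their own rule in 5.2.2. The overall-cycles rows and per-subject adverse event rates properly use the whole arm.
- *The bias has a fixed size.* It depends on the cycle and on an assumed time on treatment. Early Arm A cycles show little, and late cycles in both arms show much more.
- *Equal tolerability will print as a difference between arms.* A 2-week cycle with 7 dosing days and a 5-week cycle with 21 are different units of exposure, so equal risk per cycle is not equal tolerability. No between-arm test of these rates is planned, and a corrected denominator would not make the cycles comparable.
- *The by-cycle laboratory summaries in 7.9 have the same fault.* That section asks for summaries by grade and names no proportion.

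**Conclusion.** Wrong as written, but limited to a descriptive table. The default denominator in SAP 5.2.1.2 and 5.2.3.2, applied to the by-cycle proportions in 7.6.2, understates each rate by 1 − S(k). The direction is certain once anyone has stopped treatment, and it needs no assumption about the event rate.

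The size does rest on assumptions: exponential time on treatment, PFS medians as a stand-in for it, and cycles on schedule. Under them the understatement at cycle 2 is small in Arm A and modest in Arm B, and by cycle 6 the Arm B rates are roughly halved. Treatment can end before progression, and delays lengthen cycles; both would increase the understatement. Shortened recovery in Arm B would reduce it.

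The OS test, significance levels, power and sample size are untouched.

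**What to change.** In SAP 7.6.2, with a cross-reference in 5.2.3.2, state that by-cycle proportions use the number of subjects in the arm who started that cycle as denominator, and that this number is printed beside each cycle. Keep the full-arm denominator for the overall-cycles rows. If percentages are printed in the by-cycle grade summaries of 7.9, base them on the subjects with a value in that cycle, and say so there.

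The cost is one sentence with its cross-reference and a changed denominator in the table programs. The counts are already planned under 7.6.6, so no new data are needed. The drawback is small: late-cycle percentages will rest on fewer subjects and vary more, which the printed number makes visible.
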